12. STATISTICAL METHODS AND SAMPLE SIZE DETERMINATION

The analysis of data will be based on different subsets according to the purpose of analysis, ie, for safety and PK, respectively.

12.1 Description of analysis sets

12.1.1 Safety analysis set

All subjects who received at least 1 dose of investigational product, and for whom any postdose data are available will be included in the safety population.

12.1.2 Pharmacokinetic analysis set

The PK analysis set will include all subjects who received at least 1 dose of ceftaroline fosamil and have at least 1 measured concentration of any of the 3 analytes in plasma or dialysate at a scheduled time point after the start of the infusion. The PK analysis set should include all evaluable data appropriate for the evaluation of interest (with no major protocol deviations, violations, or events thought to significantly affect the PK of the investigational product) from all subjects who receive investigational product.

12.2 Methods of statistical analyses

12.2.1 General principles

The PK and safety summaries, individual figures, and data listings as well as the statistical analysis of PK variables will be the responsibility of the study biostatistician at Quintiles Inc., Overland Park, Kansas, USA (using SAS[®] Version 9.2 or higher and, where appropriate, additional validated software). Graphics may be prepared with SAS[®] Version 9.2, or higher; or SigmaPlot[®] 9.0, or higher (Systat Software Inc., San Jose, California, USA).

Data will generally be listed and summarised by renal function group (and further stratified by period for ESRD patients). Continuous variables will be summarised using descriptive statistics (N for sample size and n for available data, mean, standard deviation [SD], minimum, median, and maximum). Pharmacokinetic variables (concentrations, and PK parameters, except for t_{\max}) will also include geometric mean and geometric coefficient of variation (CV%). Means, SD, and CV% will not be reported for t_{\max} . Pharmacokinetic concentration data will also include lower and upper SD bounds which are defined as $\exp(m \pm s)$ where m and s are the mean and SD, respectively, of the natural log-transformed data.

The geometric mean is calculated as the exponential of the arithmetic mean calculated from data on a log scale. The CV% is calculated as $100 \cdot \sqrt{(\exp(s^2) - 1)}$ where s is the SD of the data on a log scale.

Categorical variables will be summarised in frequency tables (frequency and proportion) by renal function group.

In general, Quintiles Global Standard Operating Procedures will be followed.

Baseline characteristics will be summarised across all subjects.

12.2.2 Safety

All safety data (scheduled and unscheduled) will be presented in the data listings.

Safety variables (ie, clinical laboratory values and vital signs) will be reported to the same precision as the source data. Derived variables will be reported using similar precision to those from which they were derived.

Extra measurements (such as unscheduled or repeat assessments) will not be included in the descriptive statistics, but will be included in data listings. All AEs and clinical laboratory outliers that occur following the first dose of investigational product will be included in the tabulations of AEs and outlier events, including episodes that occur at unscheduled evaluations.

The ECG data will only be listed.

All available data from subjects in the safety analysis set will be included in the safety analyses. No adjustment or imputation will be utilised for missing values or for subjects who withdraw prior to completing the study, neither will analyses be restricted to subjects with complete data.

All SAEs will be collected for each subject from when informed consent is obtained until the follow-up visit. All AEs will be collected from Day 1 until the follow-up visit. Adverse events that occur before dosing will be reported separately.

The AEs will be summarised by Preferred Term and System Organ Class using MedDRA vocabulary (version 12.0 or higher) by renal function group and across all renal function groups. Furthermore, listings of SAEs and AEs that led to withdrawal will be made and the number of subjects who had any AEs, SAEs, AEs that led to withdrawal, and AEs with severe intensity will be summarised.

12.2.3 Pharmacokinetic analyses

Individual PK blood and dialysate sample collection times, as well as derived sampling time deviations, and concentration-time data will be listed.

Pharmacokinetic data will be presented by analyte, renal function group, and period, as appropriate.

Plasma concentrations will be summarised by nominal time points using descriptive statistics.

Plasma concentrations that are below the lower limit of quantification (LLOQ) will be handled as follows:

- At a time point where less than or equal to 50% of the values are BLQ, all BLQ values will be set to LLOQ, and all descriptive statistics will be calculated
- At a time point where more than half of the values are BLQ, the mean, SD, geometric mean, and CV% will be set to Not determined (ND). The maximum value will be reported from the individual data, and the minimum and median will be set to BLQ
- If all values are BLQ at a time point, no descriptive statistics will be calculated for that time point. Not applicable (NA) will be written in the field for SD and CV% and BLQ will be written in fields for mean, geometric mean, minimum, median, and maximum
- The number of BLQ values (n below LLOQ) will be reported for each time point

Individual plasma concentration-time profiles of the analytes will be depicted on linear and semi-logarithmic scales, showing all analytes on a single plot for each patient, and also for all patients on a single plot for each analyte. Geometric mean plasma concentration-time profiles (with lower/upper SD bounds as defined in Section 12.2.1) of each analyte will be depicted on linear and semi-logarithmic scales. For Group 1 Period 2, the full concentration-time profiles will include predialyser concentrations collected during haemodialysis and concentrations from other time points while postdialyser concentrations will be plotted separately.

Plasma and dialysate PK parameters will be summarised by analyte, renal function group, and period, as appropriate, using descriptive statistics. Figures of observed and dose-normalised C_{max} , AUC, and $AUC_{(0-t)}$ will be presented by analyte for visual comparisons of systemic exposures in healthy volunteers and in ESRD patients under nondialysis and dialysis conditions. Additional plots may be produced for graphical presentations of data as deemed appropriate.

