PROTOCOL SYNOPSIS

An Open-label, Nonrandomised, Phase I Study to Assess the Pharmacokinetics of Ceftaroline After Intravenous Administration of a Single Dose of Ceftaroline Fosamil (200 mg) to Patients with End-stage Renal Disease Undergoing Haemodialysis when Compared to a Single Dose of Ceftaroline Fosamil (600 mg) to a Matched Control Population with Normal Renal Function

Study centre(s) and number of subjects planned

This study will be conducted at 1 study centre in the United Kingdom. A minimum of 8 healthy volunteers and 8 patients with end-stage renal disease will be enrolled at the study centre.

Study period		Phase of development
Estimated date of first subject enrolled	Q3 2012	Clinical Pharmacology (1)
Estimated date of last subject completed	Q1 2014	

Objectives

Primary objective

To characterise the pharmacokinetics of ceftaroline after intravenous infusion of ceftaroline fosamil in patients with end-stage renal disease and a matched control population with normal renal function and to characterise the clearance of ceftaroline by haemodialysis.

Secondary objectives

1. To evaluate the safety and tolerability of a single intravenous infusion of ceftaroline fosamil in patients with end-stage renal disease undergoing intermittent haemodialysis
2. To characterise the pharmacokinetics of ceftaroline fosamil (the prodrug of ceftaroline) and ceftaroline M-1 (the microbiologically inactive metabolite of ceftaroline) after intravenous infusions of ceftaroline fosamil, in patients with end-stage renal disease undergoing intermittent haemodialysis and a matched control population with normal renal function

Study design

This is an open-label, nonrandomised, Phase I, single dose, study to assess the pharmacokinetics, safety, and tolerability of ceftaroline in 8 patients with end-stage renal disease requiring intermittent haemodialysis (Group 1). A group of 8 healthy volunteers with normal renal function and similar demographics (Group 2) will be recruited to provide within-study reference data.

The study will consist of a screening period (Day -28 to Day -2), residential period (2 treatment periods, Day -1 to Day 3 [Group 1] or 1 treatment period, Day -1 to Day 2 [Group 2]), and a follow-up period (7 to 10 days after discharge from the study centre).

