11.2 Calculation or derivation of pharmacokinetic variables

Pharmacokinetic analyses of the plasma concentration data for ceftaroline fosamil (the prodrug of ceftaroline), ceftaroline, and ceftaroline M-1 (the metabolite of ceftaroline) and of ceftaroline and ceftaroline M-1 concentrations in dialysate will be performed at Quintiles Inc., Overland Park, Kansas, USA. Quintiles Standard Operating Procedures and Work Instructions will be used as the default methodology if not otherwise specified. The actual sampling times (in unit of hour) will be used in the plasma PK parameter calculations.

Pharmacokinetic parameters will be derived using noncompartmental methods with WinNonlin[®] Professional Version 5.2, or higher, (Pharsight Corp., Mountain View, California, USA). All PK computations will be performed using WinNonlin[®] Professional Version 5.2, or higher; or SAS[®] Version 9.2, or higher (SAS Institute Inc., Cary, North Carolina, USA).

For missing samples or samples collected close to but not exactly at the end of the infusion, ceftaroline fosamil concentrations at the end of infusion will not be imputed unless warranted by the data. If a concentration of ceftaroline fosamil at the end of infusion needs to be estimated, the imputation will be in accordance with procedures described in Quintiles Standard Operating Procedures. The decision to impute a missing end of infusion value will be made on a case-by-case basis and documented in the CSR. In brief, the estimation steps are as follows:

1. Analyse the concentration-time data using an intravenous bolus model by setting the end of infusion time as the dosing time
2. Back-extrapolate the concentration at the time of dosing (ie, the end of infusion concentration)
3. Augment the original concentration-time data set by inserting the back-extrapolated end of infusion concentration
4. Process the augmented data set with an intravenous infusion model

Any imputed values for ceftaroline fosamil will solely be used for PK parameter calculations and will not be included in any summary or inferential statistics. Imputed values will be reported in the CSR. Imputations for the end of infusion concentrations will not be performed for ceftaroline and ceftaroline M-1.

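### The exposure comparisons between ESRD patients and controls, and between dialysis and non-dialysis periods, have no planned ratio or confidence interval and do not use the within-patient pairing

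*Protocol*

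**What the plan says.** The title is comparative: ESRD patients at 200 mg are studied "when Compared to a Single Dose of Ceftaroline Fosamil (600 mg) to a Matched Control Population with Normal Renal Function". Section 3.2 matches the controls on age, weight and gender, and Section 3.1 doses each ESRD patient twice, once between dialysis sessions (Period 1) and once just before dialysis (Period 2).

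The stated analysis in Section 12.2.3 has two parts.

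- Tables: "Plasma and dialysate PK parameters will be summarised by analyte, renal function group, and period, as appropriate, using descriptive statistics". Section 12.2.1 adds the geometric mean and geometric CV% for PK variables.
- Figures: for the main exposure measures (Cmax and the two AUCs to infinity and to the last quantifiable time), with and without dose normalisation, the plots "will be presented by analyte for visual comparisons of systemic exposures in healthy volunteers and in ESRD patients under nondialysis and dialysis conditions".

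The synopsis says the same: listings, descriptive statistics and graphs. Section 11.2 says that imputed end-of-infusion values "will not be included in any summary or inferential statistics", but no inferential analysis is described anywhere in the protocol. The only ratios defined are metabolite or prodrug ratios within one subject.

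On baseline data, Section 12.2.1 says "Baseline characteristics will be summarised across all subjects". The same section says that data are in general summarised by renal function group, and that "Categorical variables will be summarised in frequency tables (frequency and proportion) by renal function group".

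**The concern.** A study with a matched control group and two periods per patient is built to estimate two contrasts: ESRD against normal renal function, and dialysis against no dialysis. The plan gives the components of each contrast but not the contrast itself or its uncertainty.

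The protocol reasons in such ratios when it looks back. Section 1.1 reports the earlier ESRD study as percentage increases over controls. Section 3.2 uses those increases to argue that exposure at 200 mg in ESRD should not exceed exposure at 600 mg in controls. The new study is the natural place to check that statement, yet no estimate with an interval is planned for it.

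Summarising Period 1 and Period 2 separately also leaves the pairing unused. The two summaries may not rest on the same patients: the PK analysis set requires only one dose (Section 12.1.2), and withdrawals need not be replaced once six patients have completed both periods (Section 5.8.1).

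**Working it through.** The protocol states no CV, power or precision figure (Section 12.3 gives 6 subjects as sufficient and 8 recruited, with no formal basis), so there is no planned figure to reproduce. The check asks what the missing interval would look like.

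**Step 1. Projected as-dosed AUC ratio, Period 1 against Group 2.** Section 1.1 gives ceftaroline AUC after post-dialysis dosing as 167% above controls at equal dose, that is a ratio of 2.67. Post-dialysis dosing corresponds to Period 1. Section 1.1 describes exposure as roughly dose-proportional, so the ratio is scaled by dose:

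2.67 × 200/600 = 0.89.

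Two other figures in Section 3.2 agree with this. The 2.6-fold increase gives 2.6 × 200/600 = 0.87. The 80% excess of 400 mg in ESRD over 600 mg in controls gives 1.80 × 200/400 = 0.90.

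**Step 2. Interval for the unpaired contrast.** On the log scale the half-width is t(0.95, 2n−2) × s × √(2/n), with s = √ln(1+CV²). Here t = 1.761 for n = 8 and 1.812 for n = 6. The CVs are assumptions.

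| CV | n = 8: factor | 90% CI around 0.89 | n = 6: factor | 90% CI around 0.89 |
|---|---|---|---|---|
| 20% | 1.19 | 0.75–1.06 | 1.23 | 0.72–1.09 |
| 30% | 1.30 | 0.69–1.15 | 1.36 | 0.65–1.21 |
| 40% | 1.40 | 0.63–1.25 | 1.50 | 0.59–1.33 |

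Example: n = 8, CV 20%: s = √ln(1.04) = 0.198; half-width = 1.761 × 0.198 × 0.5 = 0.174; factor = exp(0.174) = 1.19.

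Every interval includes 1. For the upper limit to fall below 1, the factor must be under 1/0.89 = 1.124, with log 0.1165. That needs s below 0.1165/(1.761 × 0.5) = 0.132, a CV of about 13%, with n = 8. With n = 6 it needs s below 0.1165/(1.812 × 0.577) = 0.111, a CV of about 11%.

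**Step 3. The same check for Cmax.** From Section 3.2, 1.04 × 200/400 = 0.52, or 1.77 × 200/600 = 0.59. Even the widest factor gives 0.59 × 1.50 = 0.89, below 1. On these figures the as-dosed question is open for AUC, not for Cmax.

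**Step 4. The paired contrast, Period 2 against Period 1.** The half-width is t(0.95, n−1) × s × √(2/n), with s from the within-patient CV. At assumed within-patient CVs of 10%, 20% and 30% the 90% factors are 1.10, 1.21 and 1.32 with n = 8, and 1.12, 1.26 and 1.41 with n = 6. The contrast can be estimated at the planned size.

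**The case against.** The strongest defence is that the plan fits its aims. The objective is to characterise the PK, the controls are called reference data, the study is exploratory, and Section 3.2 says administration guidelines will come from projecting single-dose data to steady state rather than from a tested ratio. A statistical analysis plan that is not shown may add intervals. This argues against a hypothesis test and against treating the point as a fatal flaw. It does not argue against an estimate: a ratio with an interval is itself descriptive. The protocol also does more than leave the comparison open, since it states that the comparison is visual.

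Several stronger readings are tempting, and the documents do not support them.

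- *Everything is judged by eye.* Geometric means and CV% are tabulated by group and period, and individual parameters are listed, so a crude ratio can be worked out. What is absent is a planned ratio, its interval and the paired estimate.
- *The dialysis effect is not quantified.* Section 11.2 derives dialysate amount, percentage recovered, extraction and dialysis clearance by two methods. That serves the dialysis part of the primary objective. Only the between-period exposure ratio lacks an estimate.
- *At this size no real change could be told from noise.* At equal dose the earlier AUC ratios were 1.89 and 2.67. Divided by the widest factor, 1.50, the lower limits are 1.26 and 1.78, both above 1. The uncertainty bites on the as-dosed contrast.
- *Ignoring the pairing costs a known loss of precision.* A figure of about 1.8 times wider on the log scale follows if one assumes a within-patient CV of 15% against a total CV of 30%. Neither CV is in the protocol, and the protocol plans no unpaired interval to compare with.
- *Baseline data are deliberately pooled, so matching cannot be checked.* The baseline sentence does not exclude a by-group summary, and the general rules of the same section call for one. Nor does the protocol say that the baseline table is meant to demonstrate matching. The wording is ambiguous.

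**Conclusion.** The point holds in limited form. As written, the comparison across groups and periods consists of separate summaries and plots, with no ratio, no interval and no paired contrast, in a study whose title, matched controls and two-period design all point to those contrasts.

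The practical consequence is clearest for the Section 3.2 expectation about 200 mg in ESRD against 600 mg in controls. The projected AUC ratio of about 0.89 lies close enough to 1 that its 90% interval includes 1 at every CV tried from 20% to 40%, with 6 or 8 per group. This rests on dose proportionality, on the earlier study's ratio carrying over, and on assumed CVs; a CV below about 11% to 13% would be needed to change it. It says nothing about whether the doses are appropriate. It shows only that point summaries and plots would hide how firmly the data support the stated expectation.

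This is a worthwhile improvement to the stated method, not an error in any figure. The baseline sentence is a minor clarification.

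**What to change.** In Section 12.2.3, add geometric mean ratios with 90% confidence intervals for log-transformed Cmax, AUC and AUC(0-t) of ceftaroline and ceftaroline M-1, labelled as estimation only with no hypothesis test:

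- (a) Group 1 Period 1 against Group 2, unpaired, both as dosed (200 mg against 600 mg) and dose-normalised;
- (b) Group 1 Period 2 against Period 1, paired, in patients with data from both periods.

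State the number of subjects in each contrast. Keep the existing tables and figures.

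In Section 12.2.1, say that baseline characteristics are summarised by renal function group as well as across all subjects.

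The cost is one extra table and a few lines of code, with no new data, samples or subjects. The small downside is that the intervals will be wide, so the report must present them as a measure of precision and not as a failed test.

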12.3 Determination of sample size

Due to the exploratory nature of the study, the sample size is not based on formal statistical considerations. A sample size of 6 subjects is considered sufficient to characterise the PK of each dose. The study will recruit 8 subjects per group as a contingency against dropouts.

12.4 Data monitoring committee (Not applicable)

13. IMPORTANT MEDICAL PROCEDURES TO BE FOLLOWED BY THE INVESTIGATOR

13.1 Medical emergencies and AstraZeneca contacts

The principal investigator is responsible for ensuring that procedures and expertise are available to handle medical emergencies during the study. **A medical emergency usually constitutes an SAE and is to be reported as such, see Section 6.3.4.**

In the case of a medical emergency the investigator may contact the Clinical Pharmacology Alliance physician. If the Clinical Pharmacology Alliance physician is not available, contact the Clinical Pharmacology Alliance Programme Director at the AstraZeneca.

Name	Role in the study	Address & telephone number
_____		_____

13.2 Overdose

- An overdose with associated AEs is recorded as the AE diagnosis/symptoms on the relevant AE modules in the CRF and on the Overdose CRF module
- An overdose without associated symptoms is only reported on the Overdose CRF module

If an overdose on an AstraZeneca investigational product occurs in the course of the study, then the investigator or other study centre staff will inform appropriate AstraZeneca representatives **within 1 day**, ie, immediately but no later than **the end of the next business day** of when he or she becomes aware of it.

The designated AstraZeneca representative will work with the investigator to ensure that all relevant information is provided to the AstraZeneca Patient Safety data entry site.

No specific information is available on the treatment of an overdose with ceftaroline. There were no reports of an acute overdose of ceftaroline in clinical studies. In the event of an acute overdose, ceftaroline should be discontinued and general supportive treatment administered. Ceftaroline can be removed by haemodialysis. In patients with ESRD administered 400 mg of ceftaroline fosamil, the mean total recovery of ceftaroline in the dialysate following a 4-hour haemodialysis session started 4 hours postdose was 76.5 mg (21.6% of the dose). However, no information is available on the use of haemodialysis to treat an overdose of ceftaroline.

For overdoses associated with an SAE, standard reporting timelines apply, see Section 6.3.4. For other overdoses, reporting should be done within 30 days.

13.3 Pregnancy

All outcomes of pregnancy should be reported to AstraZeneca.

13.3.1 Maternal exposure

Women of childbearing potential are not allowed to be included in this study. Should a pregnancy still occur, the investigational product should be discontinued immediately and the pregnancy reported to AstraZeneca.

Pregnancy itself is not regarded as an AE unless there is a suspicion that the investigational product under study may have interfered with the effectiveness of a contraceptive medication. Congenital abnormalities/birth defects and spontaneous miscarriages should be reported and handled as SAEs. Elective abortions without complications should not be handled as AEs. The outcome of all pregnancies (spontaneous miscarriage, elective termination, ectopic pregnancy, normal birth, or congenital abnormality) should be followed up and documented even if the subject was discontinued from the study.

If any pregnancy occurs in the course of the study, then the investigator or other study centre staff should inform appropriate AstraZeneca representatives **within 1 day** ie, immediately but no later than the **end of the next business day** of when he or she becomes aware of it.

The designated AstraZeneca representative will work with the investigator to ensure that all relevant information is provided to the AstraZeneca Patient Safety data entry site within 1 or 5 days for SAEs, see Section 6.3.4, and within 30 days for all other pregnancies.

The same timelines apply when outcome information is available.

